2.5 Treatment Group Assignments or Randomization

Patients will be randomly assigned to 1 of the 4 dose levels of ENV515 within each investigative site. The contralateral eye will receive TRAVATAN Z.

The randomization code for this study will be generated by Envisia or its designee. The subjects, investigators, site staff, and project teams at Envisia and the contract research organization will be unmasked to treatment assignment.

2.6 Sample Size Determination

Since this trial is primarily a dose-finding safety and tolerability study and the first study of ENV515 in human subjects, sample size estimation was not performed. This study will enroll up to 4 arms of 2-115 subjects treated unilaterally for a maximum possible 20 subjects.

The proposed number of subjects is typical for a Phase 1/2a clinical trial and should be sufficient to assess the safety and tolerability of the study drug. Assuming that 5 subjects receive pooled active drug within a cohort, the probability of failing to observe a toxicity can be determined for various true underlying toxicity rates from the binomial distribution (Table 1). For example, for a true underlying toxicity rate of 30%, the probability of failing to observe toxicity with 5 subjects would be 0.17. For a true toxicity rate of 40%, the probability of failing to observe toxicity of failing to observe toxicity would be 0.08.

Table 1:Toxicity Probabilities (n = 5)

True Toxicity Rate (%)	10%	20%	30%	40%	50%	60%	70%	80%	90%
Probability of Failing to Observe Toxicity	0.59	0.33	0.17	0.08	0.03	0.01	0.002	<0.001	<0.001

Due to the study design and discontinuation criteria in the protocol, subjects who receive the ENV515 dose of study treatment and discontinue from the study for any reason will not be replaced.

3. GENERAL ANALYSIS AND REPORTING CONVENTIONS

The following is a list of general analysis and reporting conventions to be applied for this study.

- Categorical variables will be summarized using counts (n) and percentages (%) and will be presented in the form "n (xx.x)". To ensure completeness, summaries for categorical and discrete variables will include all categories, even if no subjects had a response in a particular category.
- Continuous variables will be summarized using mean, standard deviation (SD), minimum, maximum, median, and number of subjects. The mean and median will be reported to one more level of precision than the original observations, and the SD will be reported to 2 more levels of precision than the original observations. The minimum and maximum will be the same precision as the original data.
- All exploratory statistical tests will be 2-sided and nominal significance will be determined at the 0.05 level. All p-values will be rounded to 3 decimal places; p-values that round to "0.000" will be presented as "< 0.001".
- All analyses will be performed using SAS® System version 9.2 or higher.
- Dates will be displayed as ddmmmyyyy (e.g., 24Jan2005).

Since this study has not been powered to allow formal hypothesis testing of toxicity rates or efficacy between dose groups, any examination of treatment differences will be exploratory in nature. For all analyses, subject-level covariates will be summarized within each group by treatment (Table 2). Eye-level covariates will be summarized for each cell in the final row of Table 3.

Table 2:Subject-Level Analyses

Group 1	Group 2	Group 3	Group 4
2 implants ENV515-3	3 implants ENV515-3	1 implant ENV515-1	2 implants ENV515-1
(28.2 µg travoprost)	(42.3 µg travoprost)	(42.5 µg travoprost)	(85.0 µg travoprost)

Table 3:Eye-Level Analyses

Group 1			Group 2	Group 3		Group 4	
2 implan	2 implants ENV515-3 3 implants ENV515-3		1 implant ENV515-1		2 implants ENV515-1		
(28.2 µg	(28.2 µg travoprost)		(42.3 µg travoprost)		(42.5 µg travoprost)		g travoprost)
ENV515-3	TRAVA-TAN Z	ENV515-3	TRAVA-TAN	ENV515-1	TRAVA-TAN Z	ENV515-	TRAVA-TAN
SE	NSE	SE	Z NSE	SE	NSE	1 SE	Z NSE

SE: Study eye; NSE: Non-study eye

4. ANALYSIS POPULATIONS

Intent-to-Treat (ITT) Population

The ITT population will consist of all subjects who are randomized, receive active study drug, and complete at least one post-baseline IOP assessment.

Per Protocol (PP) Population

The PP population will consist of all subjects in the ITT population who complete all study visits and are reasonably compliant with the protocol. Any exclusions from the PP population will be determined prior to database lock.

Safety Population

The Safety population will consist of all subjects who receive at least one dose of study medication.

5. STUDY PATIENTS

5.1 Disposition of Patients

The disposition of subjects will be summarized for all subjects randomized. The number and percentage of subjects in each analysis population, the number and percentage of subjects who complete the study, as well as the number and percentage that discontinue the study and the reasons for study discontinuation will be summarized by dose group.

5.2 **Protocol Deviations**

All protocol deviations will be recorded and reported in listings. Major protocol deviations will be identified prior to database lock.

6. DEMOGRAPHIC AND OTHER BASELINE CHARACTERISTICS

Baseline demographic characteristics such as age and gender and clinical characteristics including VA, IOP, gonioscopy, and corneal thickness will be summarized using descriptive statistics. Baseline will be defined as the last measurement prior to administration of the first dose of study drug. Demographics will be summarized at the patient level, while baseline clinical characteristics will be summarized by study eye and non-study eye. All demographics and baseline clinical characteristics will be listed.

7. MEASUREMENTS OF TREATMENT COMPLIANCE

In this study, the principal investigator administers the investigational treatment into the study eye on the day of randomization. As a result, compliance with the investigational product will be 100%. Compliance information will not be collected for the active control, TRAVATAN Z.

8. EFFICACY EVALUATION

8.1 Overview of Efficacy Analysis Issues

8.1.1 Handling of Dropouts or Missing Data

No adjustments for missing values will be made. Missing values will be noted in the CSR.

8.1.2 Assessment Time Windows

Intraocular pressure will be measured at visit 2 (day -7 to -1) and visit 8 (day 25 ± -1 day). It will be collected at times 8AM, 10AM and 4PM (all times are ± -30 minutes).

8.2 Efficacy Variables

The efficacy parameter measured in this study is the IOP time-matched change from pre-dose baseline. The diurnal curve measurements will be made at the Baseline Visit and at Visit 8 (Day 25) and will be collected in both eyes at 8AM, 10AM, and 4PM. Time-matched change from baseline will be calculated separately for each time point at Visit 8 (i.e., 8AM Visit 8 – 8AM Baseline, 10AM Visit 8 – 10AM Baseline, and 4PM Visit 8 – 4PM Baseline).

Three consecutive measurements will be taken at each time point to determine IOP. All three measurements will be recorded and the median IOP of the three measurements will be recorded and used in the analysis for that time point.

Additionally, as a safety measure, IOP is also collected in both eyes at 8AM at all other visits.

8.3 Analysis Methods

8.3.1 Primary Efficacy Analyses

The efficacy parameter measured in this study is IOP change from pre-dose baseline. Exploratory analyses comparing the change in IOP over time between treated study pre-surgical eyes and contralateral non-study TRAVATAN Z eyes will be performed. Differences in IOP change from baseline between dose groups will be explored.

The primary endpoint will be the average IOP diurnal curve measurement change from baseline. Intraocular pressure is measured at 8 AM, 10 AM and 4 PM in 3 replicates. The median of the replicates at each of these times will be averaged over the time points to calculate the average IOP diurnal curve measurement. If there were no measurements at either the 8 AM, 10 AM or 4 PM times, then the average IOP diurnal curve measurement will be missing.

Descriptive summary statistics will be presented for average IOP diurnal curve by dose group, study eye and non-study eye, and visit. Descriptive statistics will include mean,

standard deviation, median, interquartile range, minimum and maximum. Both change from baseline and percent change from baseline will be summarized.

Change from baseline in average IOP diurnal curve will be analyzed using an ANCOVA by treatment group and controlling for baseline. This will be done separately for the study eye and non-study eye. Estimates of the slope for each treatment group will be examined along with corresponding p-values for the estimates being non-zero. See Appendix 13.2 for more information.

8.3.2 Other Efficacy Analyses

Descriptive summary statistics will be presented for IOP diurnal curve by dose group, study eye and non-study eye, visit and time point. A comparison of the IOP diurnal curve between treatments will be made. Time-matched change from baseline and percent change from baseline in IOP at each time point for Day 25 will be summarized descriptively. Descriptive statistics will include n, mean, standard deviation, median, minimum, maximum and inter-quartile range.

Time-matched change from baseline in IOP diurnal curve will be analyzed using an ANCOVA controlling for treatment group and time-matched baseline. This will be done separately for each time point and for study eye and non-study eye. The purpose of this analysis will be to examine whether treatment was able to reduce IOP at every time point. Therefore, estimates of the slope for each treatment will be examined along with corresponding p-values for the estimates being non-zero. The See Appendix 13.2 for more information.

Time-matched change from baseline in IOP comparing the treated study-eye with the non-treated study eye will be examined using a paired t-test. This will be done separately for each treatment group and time point. Mean differences and 95% confidence intervals between study eye and non-study eye will be presented.

Summary statistics by time point and study eye and non-study eye will also be presented.

Comparisons of IOP measurements collected at 8AM at all visits will be examined. Summary statistics by visit and study eye versus non-study eye will also be presented. Baseline will be calculated by averaging the 8AM measurements taken at Visit 2 and Visit 3. If subjects had not washed out sufficiently at Visit 2, then they were to come in for an unscheduled visit to have IOP measured. In these cases, baseline will be the average of the Unscheduled Visit and Visit 3. The change from baseline IOP at 8 AM values in the study eye will be analyzed using an ANCOVA with treatment and baseline IOP in the model. This will be done separately for each time point. A similar ANCOVA will be fit for the non-study eye. This analysis will examine the estimates for each treatment group as well as an overall estimate across treatment groups to determine if the estimates are non-zero. Paired t-tests will be done for each treatment group comparing the change from baseline in the study-eye and non-study eye

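### The Cohort 1 SAP replaces an insufficiently washed-out Visit 2 only in the 8 AM series, so the primary diurnal change keeps Visit 2 as its baseline

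*SAP*

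**What the plan says.** The Cohort 1 SAP defines the primary endpoint in 8.3.1: "The primary endpoint will be the average IOP diurnal curve measurement change from baseline". The average is formed over 8 AM, 10 AM and 4 PM. Section 8.3.1 names no baseline visit, but 8.1.2 does: "Intraocular pressure will be measured at visit 2 (day -7 to -1) and visit 8". Section 8.2 also places the pre-dose diurnal curve at the Baseline Visit, and adds: "Time-matched change from baseline will be calculated separately for each time point at Visit 8". None of these sections mentions an unscheduled visit or incomplete washout.

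Section 8.3.2 then describes a separate analysis: "Comparisons of IOP measurements collected at 8AM at all visits will be examined". It has its own baseline: "Baseline will be calculated by averaging the 8AM measurements taken at Visit 2 and Visit 3". For subjects whose washout at Visit 2 was insufficient and who returned to be measured again, it says: "In these cases, baseline will be the average of the Unscheduled Visit and Visit 3".

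Section 6, on baseline characteristics, carries a general definition: "Baseline will be defined as the last measurement prior to administration of the first dose of study drug".

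**The concern.** Section 8.3.2 treats the Visit 2 pressure of certain subjects as unfit to serve as baseline. The replacement reaches a supporting analysis and stops there. An analyst who follows the text would use the rejected visit for those same subjects in the primary endpoint and in the time-matched analyses.

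A baseline taken while earlier medication is still acting is too low, so the fall to Day 25 looks smaller than it is. The arms had 2, 2, 7 and 10 patients (Protocol 1.4.1, Table 9), so one subject carries visible weight in an arm mean and in the comparison between dose groups.

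**Working it through.** **Where each rule applies**

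| Analysis | Baseline in the SAP | Replacement for insufficient washout |
|---|---|---|
| Primary: average diurnal change (8.1.2, 8.2, 8.3.1) | Visit 2 curve | none stated |
| Time-matched change at 8 AM, 10 AM, 4 PM (8.2, 8.3.2; Tables 12–14) | Visit 2, same clock time | none stated |
| 8 AM at all visits (8.3.2; Tables 15–17) | mean of Visits 2 and 3 | mean of Unscheduled Visit and Visit 3 |

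The plan states no figure on this point, so there is none to reproduce.

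**Effect on the primary.** If k of n subjects in an arm have a Visit 2 diurnal average that is b mmHg too low, the mean reduction in that arm is understated by k × b / n. The arm sizes are from Protocol 1.4.1. The documents give neither k nor b, so k = 1 and b = 2 to 6 mmHg are assumptions.

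- Low-dose ENV515-3, n=7: 2/7 = 0.29 to 6/7 = 0.86 mmHg, against a reported mean change of -5.1 (Protocol 1.4.2).
- High-dose ENV515-3, n=10: 2/10 = 0.2 to 6/10 = 0.6 mmHg, against -6.7.
- Each ENV515-1 arm, n=2: 2/2 = 1 to 6/2 = 3 mmHg.
- k = 0: no change in any arm.

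The reported ENV515-3 means differ by 6.7 − 5.1 = 1.6 mmHg. One affected low-dose subject would shift that difference by 0.29/1.6 = 18% to 0.86/1.6 = 54% of its size.

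These shifts apply to raw mean changes. The ANCOVA adjusts for the same baseline, so its estimates would shift by a different amount. The documents report no slope, so I have not computed it.

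**Can the reported results show which baseline was used?** Dividing mean change by mean percent change gives approximate baselines of 5.1/0.213 = 23.9, 6.7/0.279 = 24.0 and, for TRAVATAN Z, 6.6/0.280 = 23.6 mmHg. These do not identify the visit.

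**Can the 8 AM replacement be copied to the diurnal average?** Not always. Protocol 5.12 requires one IOP reading at an unscheduled visit, in the study eye only. SAP 8.3.1 sets the diurnal average to missing when a time point is absent. A replacement therefore needs a full repeat curve, and the fellow eye may have no repeat value.

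**The Day 25 8 AM change.** Visit 8 at 8 AM falls in both the time-matched analysis and the 8 AM series. For a washed-out subject the two changes differ by (Visit 3 − Visit 2)/2. Illustrations with assumed pressures:

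- Washed out, Visit 2 = 24, Day 25 = 18. Time-matched change: 18 − 24 = -6. In the 8 AM series: 18 − (24 + 22)/2 = -5 if Visit 3 is 22, or 18 − (24 + 26)/2 = -7 if it is 26.
- Not washed out but at the lower entry limit, Visit 2 = 22, Unscheduled = 25, Visit 3 = 25, Day 25 = 18. Time-matched change: 18 − 22 = -4. In the 8 AM series: 18 − (25 + 25)/2 = -7.

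**The case against.** The best defence is that the SAP is silent here and never instructs anyone to keep an unwashed curve. Protocol 4.1, criterion 7, requires 22–34 mmHg at 8 AM and 10 AM and 19–34 mmHg at 4 PM in both eyes at a post-washout Baseline Visit, and 4.3 requires the criteria still to be met at randomization. A subject held below those limits by residual drug would need a qualifying curve before dosing, and Section 6 of the SAP, if applied to efficacy, would pick the later curve. This makes a repeat curve plausible. It does not tell the analyst to use one in the primary, and a subject can reach 22 mmHg with some drug effect remaining.

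The size is also open to challenge. The number affected is unknown, and 6 mmHg is 6/6.6 = 91% of the reported TRAVATAN Z effect, so the upper end assumes almost no washout. Patients used a prostaglandin analogue in both eyes, so residual effect would tend to lower both baselines and partly cancel between eyes. Any bias in within-eye change is conservative, and all tests are exploratory. These points stand and limit the finding.

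A reader might infer that the reported Cohort 1 reductions are wrong. The documents do not support that: they identify no affected subject and do not show which curve was used. A reader might also call the two Day 25 8 AM baselines an error. Both are prespecified, and Visit 3 has only an 8 AM reading (Protocol 5.3.1), so a two-visit average cannot be formed at 10 AM or 4 PM. The Section 6 definition sits under baseline characteristics, and the specific rule in 8.3.2 governs the 8 AM series, so it is not a firm contradiction either.

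**Conclusion.** The gap in the primary analysis is real. Followed as written, the SAP keeps for its primary endpoint a baseline that it sets aside for the same subjects in a supporting analysis. The direction is clear: within-eye lowering is understated. The size is conditional. It is residual effect divided by n for each affected subject, so under the assumed 2 to 6 mmHg one subject matters modestly in the two ENV515-3 arms and more in the two-patient arms, and there is no effect if nobody was affected. The comparison with the fellow eye is less exposed than within-arm changes and dose-group comparisons. The two Day 25 8 AM baselines are a labelling matter only.

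**What to change.** 1. Where a full 8 AM, 10 AM and 4 PM curve was repeated after washout and before dosing, use it as the baseline for the average diurnal change and the time-matched changes. Apply the same rule to both eyes.
2. Where an eye has no full repeat curve, keep Visit 2 in the primary and add a sensitivity analysis without that subject.
3. Report, by arm, how many subjects had an Unscheduled Visit baseline and how many of those had a full repeat curve in each eye.
4. Footnote Tables 12–14 and 15–17 to say that they compute the Day 25 8 AM change from different prespecified baselines.

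The cost is a few lines of SAP text, a baseline derivation that checks each eye for a full repeat curve, and one extra sensitivity table with slightly fewer subjects. Cohort 1 has already been summarised in the protocol, so the change would be an addendum or a described deviation in the study report. If the count in item 3 is zero, items 1 and 2 change no result.

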9. SAFETY EVALUATION

9.1 Overview of Safety Analysis Methods

Adverse events, clinical laboratory results, vital signs, and physical exam findings will be tabulated at the subject level. All other safety measurements will be made at the eye level. Unless otherwise noted, baseline will be defined as the last measurement prior to receiving the implant.

9.2 Extent of Exposure

The number of days from implant insertion to implant removal will be summarized using means and standard deviations. The number of days from implant insertion to removal, as well as whether the subject required early removal of the implant, will be available in subject listings. Exposure will be calculated only for the study eye. No exposure information for the TRAVATAN Z eye will be collected.

9.3 Adverse Events

Adverse events (AEs) will be coded using the Medical Dictionary for Regulatory Activities (MedDRA) and categorized by system organ class using preferred terms by dose group. Events will be tabulated with respect to their intensity and relationship to the study drug. Only treatment-emergent AEs will be summarized. A treatmentemergent AE will be defined as any AE with onset date on or after the first exposure date. AEs will be tabulated separately for study eye, non-study eye and non-ophthalmic events.

All serious adverse events (SAEs) and other significant events, including withdrawals due to AEs, will be individually summarized in the CSR.

All treatment-emergent AE and SAE data will be presented in subject listings.

9.4 Clinical Laboratory Evaluation

Continuous clinical laboratory values will be summarized using means and standard deviation for reported and change-from-baseline values. Categorical clinical laboratory values will be summarized using shift tables displaying the frequencies of subjects with abnormal or normal results. Clinical laboratory results will be summarized at the subject level. In addition, clinical laboratory data will be presented in subject listings.

9.5 Vital Signs, Physical Findings, and Other Observations Related to Safety

9.5.1 Vital Signs

Vital sign assessments include measurements of heart rate, blood pressure, and respiration rate. Vital signs will be summarized by study visit and treatment group. All vital sign data will be presented in subject listings.

9.5.2 Physical Examinations

All physical examination data will be presented in listings.

9.5.3 Corneal Thickness (Pachymetry)

Pachymetry will be performed at the Screening Visit, Baseline Visit, Visit 6, Visit 8, and Visit 10. Three measurements will be taken and the average will be used in summary tables. Corneal thickness and change from baseline corneal thickness will be summarized by visit, study eye, and non-study eye. All pachymetry data, including all three measurements for each eye, will be listed.

9.5.4 Visual Acuity (VA)

Visual acuity will be measured using the Early Treatment Diabetic Retinopathy Study (ETDRS) chart according to the manufacturer's specifications at all study visits. The number of letters missed will be collected and summarized for Visit 2 and Visit 11 by study eye/non-study eye, and treatment group. In addition, the number and proportion of subjects with greater than or equal to 3 lines lost will be summarized. Three lines lost will be defined as greater than or equal to 15 letters missing. All VA data, including manifest refraction, LogMAR, and total letters missed will be presented in subject listings.

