Study Treatment Investigational Product: ENV515 (travoprost) Intracameral Implant administered into the study eye as a single, unilateral dose via intracameral injection on Day 1

Reference Product: TRAVATAN Z administered into the non-study eye

Dosage/Dose Regimen/Treatment Groups:

- 4 dose levels of ENV515 (travoprost) Intracameral Implant achieved via the following numbers and sizes of implants: 28.2 μg (2 ENV515-3 implants), 42.3 μg (3 ENV515-3 implants), 42.5 μg (1 ENV515-1 implant), and 85.0 μg (2 ENV515-1 implants).
- Control Group: TRAVATAN Z ophthalmic solution administered QD daily in the non-study, fellow eye

Rescue Therapy: Both the study and non-study eyes may be treated at any time, at the investigator's discretion, if it is considered to be in the best interest of the patient.

Randomization/Stratification: To minimize bias, patients were assigned to 1 of the 4 dose levels of ENV515 within each investigative site. The non-study eye received TRAVATAN Z.

Visit Schedule: Visit schedule encompasses Screening Visit 1 (Day -35 to -28) followed by 4-week IOP-lowering medication washout period with up to 2-week additional extension to allow full washout, Baseline Visit 2 (Day -7 to -1), Randomization/ Treatment Visit 3 (Day 1), Treatment Visit 4 (Day 3 ± 1 day), Treatment Visit 5 (Day 7 ± 1 day), Treatment Visit 6 (Day 14 ± 1 day), Treatment Visit 7 (Day 21 ± 1 day), Treatment Visit 8 (Day 25 ± 1 day), Surgery Visit 9 (Day 28 ± 1 day), Follow-up Visit 10 (Day 33 to 38 ± 1 day), and Follow-up Visit 11 (Day 42 to 49 ± 1 day) for a total of 11 visits.

Study Population Characteristics:

Number of Patients: Following successful screening, approximately 20 patients were enrolled into the study within the United States.

Condition/Disease: The study population consisted of patients with a diagnosis of bilateral ocular hypertension or primary open-angle glaucoma who were currently being treated with a topical prostaglandin analogue (PGA) in both eyes and who were scheduled for cataract surgery in their study eye.

Inclusion Criteria:

- 1. Provide written informed consent prior to study procedures.
- 2. Are between 18 and 85 years of age.
- 3. Have a willingness to comply with the investigator's instructions, attend study visits, and stop prior eye medications to treat glaucoma and/or ocular hypertension.

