The Cohort 1 phase of this study was a multicenter, randomized, open-label, parallel-group, dose-ranging, 28-day Phase 2a trial to assess the safety, tolerability, efficacy, aqueous humor PK. systemic exposure, and remaining travoprost in ENV515 implants for 4 dose levels of ENV515, and was conducted in 21 patients with bilateral open-angle glaucoma or ocular hypertension (see inclusion criteria in Section 4.1) who are scheduled for upcoming cataract surgery in a single eye. For the purposes of the Cohort 1 phase of this study, early primary open-angle glaucoma was defined as focal non-full thickness rim thinning with no VF changes or small isolated nasal step or paracentral scotoma or Seidel's scotoma with VF mean defect (MD) of MD \leq -8.0. The dose levels of travoprost in the Cohort 1 phase of this clinical study, administered via single. unilateral intracameral injection of ENV515-1 and ENV515-3 formulations, were 28.2 µg/eye, 42.3 ug/eve, 42.5 ug/eve and 85.0 ug/eve. The 4 dose level groups were achieved via the following numbers and sizes of implants: 28.2 µg (2 ENV515-3 implants), 42.3 µg (3 ENV515-3 implants), 42.5 µg (1 ENV515-1 implant), and 85.0 µg (2 ENV515-1 implants). ENV515 implants were administered unilaterally in the study eye (pre-surgical eye) 4 weeks prior to the cataract surgery and the implants were retrieved during the cataract surgery. All non-study eyes received open label TRAVATAN Z (travoprost ophthalmic solution), 0.004% per their usual treatment regimen (Figure 2).

Figure 2: ENV515 Treatment Arms, Cohort 1

ENV515 Dose Groups*

[figure not shown]
^{*} Treatment assignment of ENV515 dose level 1-4 randomized to study eye

The four ENV515 dose levels were administered in a parallel group design, with each patient participating in only one group. Following Day 25 of the treatment phase (Visit 3/Day 1 to Visit 8/Day 25 [±1 day]), analysis of IOP treatment effect at Visit 8/Day 25 (±1 day) as % change in diurnal IOP from diurnal IOP baseline was conducted as the primary efficacy outcome measure. Following the completion of the study follow-up (Visit 11/Day 42 to Day 49), all safety and tolerability assessments were conducted. The assessment of safety and tolerability

included, but was not be limited to, data from the AE reports, corneal thickness, endothelial cell morphology, endothelial cell counts, and slit lamp examination.

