5.8.1. Disbursement and First Administration of Pre-Surgical Medications

Following the completion of all assessments, the patients will receive their pre-surgical antiinflammatory and antibiotic medications: PRED FORTE, PROLENSA, and VIGAMOX. The

87

medications will be administered by the patients on Day 26, 27, and 28 twice a day for each medication, once in the morning and once in the evening. Following the removal of the ENV515 implant (Visit 9/Day 28), it is upon the discretion of the investigator to determine the post-operative medication regimen. Patients will be provided with instructions on use of these medications and what to do to prepare for their cataract surgery.

Patients are expected to remain in the clinic for the completion of all procedures (~8:00 a.m. to ~4:30 p.m.). However, at the discretion of the investigator, patients will be permitted to leave the clinic after completing the 10:00 a.m. IOP measurement and will return to the clinic before the 4:00 p.m. IOP measurement. Any patient that leaves the clinic will be instructed to return no later than 30 minutes prior to 4:00 p.m. Before patients leave the clinic for the day, they should receive an appointment for their next study visit and the instructions provided in Section 5.1.2.

5.9. Visit 9/Day 28/Cataract Surgery, Cohort 1

Query patient about changes in concomitant medications and whether or not they have experienced symptoms suggesting an AE. AEs will be documented.

5.9.1. Pre-surgery Assessment, Cohort 1

Assessments will be conducted in the following order. Both eyes will be evaluated at all ophthalmic assessments:

- 1. Assess BCVA (ETDRS) with manifest refraction
- 2. If dilation is required to properly conduct BCVA (ETDRS) with manifest refraction the assessment should be performed after the slit lamp biomicroscopy and IOP measurement.
- 3. Perform slit lamp biomicroscopy
- 4. Perform corneal staining
- 5. Measure IOP at 8:00 a.m. (±30 minutes)
- 6. Perform gonioscopy to identify the location of the ENV515 implants to facilitate implant recovery during the cataract removal procedure
- 7. Additional assessment needed prior to cataract removal conducted per discretion of the principal investigator

5.9.2. Cataract Removal Procedure Combined with Aqueous Humor Sampling and Implant Recovery, Cohort 1

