9.5.9 Visual Field

Visual field assessments will be made at the Screening Visit and Visit 10. Shift tables of normal/abnormal findings will be presented by study eye/non-study eye and treatment group. All visual field data will be listed.

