Envisia Therapeutics Protocol No. ENV515-01		CONFIDENTIAL		Statistical Analysis Plan 23SEP2015
		Urinalysis Values: Shift from Baseline to Each Visit by Treatment Group		
CT_TAA	47	Mean and Mean Change from Baseline in Corneal Thickness by Treatment Group and Visit	Safety	
EC_TAA	48	Mean and Mean Change from Baseline in Endothelial Cell Count by Treatment Group and Visit	Safety	
SL_TAA	49	Summary of Change from Baseline in Hyperemia Score by Treatment Group and Visit	Safety	
SL_TAB	50	Shift from Baseline in Slit Lamp Biomicroscopy by Visit and Treatment Group	Safety	
DF_TAA	51	Shift from Baseline in Dilated Fundus Exam Finding to Each Visit by Treatment Group	Safety	
VF_TAA	5	Shift from Baseline in Visual Field to Each Visit by Treatment Group	Safety	
VA_TAA	53	Mean and Mean Change from Baseline in Visual Acuity (EDTRS Letters Missed)) by Treatment Group and Visit	Safety	
VA_TAB	54	Proportion of Subjects with 3 or More Lines Lost by Treatment Group	Safety	
PM_TAA	55	Mean and Mean Change from Baseline in Pupil Measurement by Treatment Group and Visit	Safety	
PK_TAA	56	Summary of Pharmacokinetics and Implant Information by Treatment Group	Safety	

ŝ

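### The Cohort 1 SAP names only Visit 2 and Visit 11 for the visual acuity summary, so the tabulated study-eye change spans implant removal and cataract extraction, and the on-implant readings stay in listings

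*SAP*

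**What the plan says.** **Acuity.** SAP (2015, Cohort 1) 9.5.4 has acuity measured to the chart manufacturer's "specifications at all study visits". It then limits the summary: "The number of letters missed will be collected and summarized for Visit 2 and Visit 11 by study eye/non-study eye, and treatment group". The remaining readings are covered by a further sentence: "All VA data, including manifest refraction, LogMAR, and total letters missed will be presented in subject listings". The same section also plans the proportion of subjects losing three or more lines, without naming a visit.

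**Planned tables.** SAP section 11, Table 53, is titled "Mean and Mean Change from Baseline in Visual Acuity (EDTRS Letters Missed)) by Treatment Group and Visit". Table 54 (three or more lines lost) names no visit.

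**Visual field.** SAP 9.5.9: "Visual field assessments will be made at the Screening Visit and Visit 10". Protocol Table 1 has the same two visits.

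**Surgery.** Protocol section 3 says the implants were given "4 weeks prior to the cataract surgery and the implants were retrieved during the cataract surgery". The visit schedule puts this at Visit 9, Day 28. Section 5.9.2 describes implant recovery, cataract removal and lens implantation in one procedure. On that day acuity is still taken first, before surgery: section 5.9.1 opens with "Assess BCVA (ETDRS) with manifest refraction".

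**The concern.** Acuity and visual field are both listed safety measures for Cohort 1, to be judged by change from baseline, and safety is a primary objective. The one post-baseline acuity visit named for summary, and the only post-baseline field test, come after the implant has gone and the lens has been replaced.

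Surgery is done in the study eye only. Neither the before-and-after change nor the comparison with the TRAVATAN Z eye separates the implant from the operation, and the mixing can work in either direction:

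- An acuity loss while the implant was in place could be offset by the cataract removal. Protocol 1.4.1 and 1.4.3 report corneal edema from implant contact in this cohort.
- A surgical problem could be counted against the implant. Protocol Table 11 shows posterior capsule opacification in 2 of 10 patients in the three-implant group, footnoted as occurring after cataract removal.

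Protocol 4.1 also allows additional procedures after the extraction, and 5.9.3 allows IOP-lowering medication to be prescribed then. Both add to what the Visit 11 reading contains.

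**Working it through.** The plan gives no figure to reproduce here. The check is visit-day arithmetic and a count of readings.

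**Inputs.** Protocol Cohort 1 synopsis and Table 1: Visit 4 Day 3, Visit 5 Day 7, Visit 6 Day 14, Visit 7 Day 21, Visit 8 Day 25, Visit 9 Day 28 (surgery), Visit 10 Day 33 to 38, Visit 11 Day 42 to 49. The synopsis puts ±1 day on Visits 9, 10 and 11. Protocol 1.4.1: 21 patients randomized, treated and completed.

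**Days from surgery** = visit day − 28. For the widest range, the visit moves one day one way and surgery one day the other.

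| Visit | Nominal | With ±1 day on both |
|---|---|---|
| Visit 10 (field) | 33 − 28 = 5 to 38 − 28 = 10 | 32 − 29 = 3 to 39 − 27 = 12 |
| Visit 11 (acuity) | 42 − 28 = 14 to 49 − 28 = 21 | 41 − 29 = 12 to 50 − 27 = 23 |

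Both visits follow surgery under every permitted window.

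**Post-dose readings with the implant in place**

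| Measure | Scheduled | Named for summary |
|---|---|---|
| Acuity | 6 (Visits 4, 5, 6, 7, 8 and pre-surgery 9) | 0 |
| Visual field | 0 | 0 |

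For acuity that is up to 6 × 21 = 126 study-eye readings left to listings.

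**Consistency within the SAP**

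- Corneal thickness (9.5.3), endothelial count (9.5.5), slit lamp (9.5.6) and pupil size (9.5.7) are all summarised by visit. Acuity is the exception.
- The text of 9.5.4 (two visits) and the title of Table 53 (by visit) do not agree on layout.
- SAP 9.1 sets the safety baseline, unless otherwise noted, as the last reading before the implant. Protocol 5.3.1 takes acuity before dosing at Visit 3, so that rule gives Visit 3. Section 9.5.4 uses Visit 2 without a reason.

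**Comparability of the six readings.** Protocol 5.8.1 has patients use three pre-surgical eye drops on Days 26, 27 and 28, handed out after the Visit 8 assessments. Visit 8 is thus the last reading before those drops, and Visit 9 is taken during them.

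**The case against.** The strongest reply is that little is lost. Every acuity reading is listed, and with arms of 2, 2, 7 and 10 patients a reader can follow each eye through the listing. Table 53 may already be laid out by visit: SAP section 1 says table specifications are in separate documents, which are not available here. The event of most concern, corneal edema, is also covered while the implant is in place: by slit-lamp shift tables, by corneal thickness at Visits 6 and 8, and by study-eye adverse event tables for Days 1 to 7 and 19 to 25. The medical monitor received all ocular safety data as generated (protocol 3.1.1). Protocol 1.4.3 reports no acuity change in the two patients with endothelial cell loss, so acuity was looked at.

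Most of this stands, and it rules out several stronger readings that a reader might infer:

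- *The plan cannot show the implant's effect on vision.* That is true of the summary 9.5.4 names and of visual field. It is not true of the acuity data, which can be recovered from listings.
- *Harm would be hidden.* The other summaries make that too strong. The documents support only that the acuity table as worded would not show it.
- *The table would favour ENV515 over TRAVATAN Z.* The SAP plans no between-eye acuity test and calls all treatment comparisons exploratory. The documents give no size for a gain from cataract removal.
- *The field test should move to Visit 8.* Cohort 1 is complete, and the move would give up the only field test after intraocular surgery.

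What does not stand is that listings make the summary acceptable. A listing is not a summary by dose group, and the text as written points the programmer to a confounded contrast.

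**Conclusion.** The point holds as a moderate reporting correction. It affects all 21 study eyes in the named acuity summary and in the visual field shift table, because both post-baseline readings follow implant removal and cataract extraction. It does not affect the primary endpoint, the analysis populations or the sample size, and no acuity data are lost.

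The conclusion assumes that the text of 9.5.4 governs the output. If the separate table specifications already show every visit, what remains is a conflict between text and table, the choice of baseline and the missing surgical label. The direction and size of the confounding cannot be given from the documents.

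The point is confined to Cohort 1. The 2019 SAP for Cohorts 2 and 3 summarises acuity for each visit, and those cohorts have no scheduled surgery.

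**What to change.** In SAP 9.5.4 and Tables 53 and 54:

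1. Summarise change in letters from baseline, and loss of 15 or more letters from baseline, at each of Visits 4 to 9 (pre-surgery), by dose group and eye. Make Visit 8 (Day 25) the main on-implant comparison, and footnote that Visit 9 follows the start of the pre-surgical eye drops.
2. Use the SAP 9.1 baseline, which is the Visit 3 pre-dose reading, or state why Visit 2 is used instead.
3. Show Visits 10 and 11 under a separate heading, *after implant removal and cataract extraction*.
4. Make the text of 9.5.4 and the layout of Table 53 agree.

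For visual field (SAP 9.5.9 and its shift table), use the same heading, and do not cite the study-eye column as evidence on ENV515's effect on the field. State in the report that no field test was done with the implant in place.

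The cost is a few lines of SAP text, extra table rows from readings already collected, and one footnote. If the Cohort 1 tables have already been produced, the additions can be run as supplementary tables and identified as such in the report, which SAP section 1 allows.
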